### 3.4 Per-protocol Population

The per-protocol population will comprise all participants recruited in to the trial who had their intervention administered and who do not have major protocol deviations.

# 3.5 Safety Population

The safety population will be comprised of the all individuals that received at least one injection of either the anti-ST2 or placebo, with individuals that received any injections of the active dose being analysed in the Anti-ST2 arm, regardless of randomised allocation.

# 3.6 Other Analysis Populations

None

ST-QRD-1 v2

# 4 General Issues for Statistical Analysis

#### 4.1 Derived/Computed Variables

**Body mass index (BMI)**: This will be derived as per WHO Guidelines, BMI measures as Kg/m^2.

Age: Age will be measured in years and will be derived from the date of birth at the randomisation date.

COPD Assessment Tool (CAT) score: The CAT consists of 8 items with scores ranging from 0 to 5 (0= no impairment). An overall score will be calculated by adding the score from each item with total scores ranging from 0 to 40, higher scores indicating a more severe health status impairment or a poorer control of COPD.

St George's Respiratory Questionnaire for COPD patients (SGRQ-C): The SGRQ-C is in two parts. Part I produces the Symptoms score, and Part 2 the Activity and Impacts scores. A Total score is then produced. Each questionnaire response has a unique empirically derived `weight'. The lowest possible weight is zero and the highest is 100. A **Total** and three component scores are calculated: **Symptoms**; **Activity**; **Impacts**.

The **Symptoms** component consists of all the questions in Part 1. The weights for Questions 1-7 are summed. A single response is required to each item. If multiple responses are given to an item, then average weight should be calculated.

The **Activity** component is calculated from the summed weights for the positive responses to items Questions 9 and 12 in Part 2 of the questionnaire.

The **Impacts** component is calculated from Questions 8, 10, 11, 13, 14 in Part 2 of the questionnaire.

Then the **Total** score is calculated by summing the weights to all the positive responses in each component.

**FEV1/FVC ratio**: FEV1 is the volume of air exhaled in 1 second, FVC is FVC is the full amount of air that can be exhaled with effort in a complete breath. FEV1/FVC ratio is a measure of airflow obstruction, with values <0.7 (70%) indicating airflow obstruction.

**BD Reversibility percentage**: this will be computed as % Reversibility = (post-BD FEV1- pre-BD FEV1) × 100/pre-BD FEV1

**RV/TLC ratio:** this is the residual volume (RV) to total lung capacity (TLC). It is calculated using  $\frac{RV}{TLC} \times 100\%$ 

# 4.2 Multiple Testing

There will be no adjustment for multiple comparisons as there will be only one primary analysis.

# 4.3 Interim Analysis and Data Review

There is no interim analysis planned. The DSMC will receive report three monthly during recruitment period, then six monthly thereafter during 12 month follow-up period. The report will contain tables on recruitment, disposition of participants, trial and data quality, adverse events, and protocol deviations. There will be open and closed sessions. The open sessions will involve presentation of data relating to recruitment and retention based on pooled data and data quality (e.g data return dates, treatment compliance) blind to treatment allocation. The closed session will involve presentation of efficacy and safety data unblinded by treatment group.

Recruitment and disposition will also be presented in a Consolidated Standards of Reporting Trials (CONSORT) diagram.

# 4.4 Analysis Software

It is anticipated that the analysis will be done in STATA, R or SAS statistical software (versions will be recorded in the statistical report). The University of Leicester holds the relevant licences for this software.

# 5 Statistical Methodology

The statistical analysis will be based on relevant guidelines (e.g. ICH E3 and E9 statistical principles for clinical trials). The date of data extraction from the database will be included in each report.

# 5.1 Disposition of Patients

Patient disposition will be presented with respect to trial completion status, reason for non-completion, protocol deviations, primary outcome data completeness and length of stay in the trial (Figure 3). Results will be tabulated and summarised over time by intervention arm.

A CONSORT [1] diagram will display the flow of patients through the trial. A graph of cumulative recruitment will be presented in addition to summaries of recruitment (e.g. start and end date).

#### Figure 2: CONSORT Diagram

For detailed information on the reasons for exclusion criteria please refer to Table 3 in Appendix-1.

ST-QRD-1 v2

# 5.2 Demographic and Baseline Characteristics

Numbers (with percentages) for binary and categorical variables and means (and standard deviations), and medians (with lower and upper quartiles) for continuous variables will be presented. There will be no tests of statistical significance nor confidence intervals for differences between randomised groups on any baseline variable.

The stratification variable will be summarised by treatment arm in order to check the balance of the low and high frequency of moderate to severe exacerbation in the previous 12 months prior to the study between the two randomised arms.

The baseline variables that will be summarised are included in Table 4 in Appendix-1.

# 5.3 Comparison of losses to follow-up

The numbers (with percentages) of losses to follow-up, withdrawals and discontinuation of study treatment will be reported descriptively between the intervention and placebo arms. Any deaths (and their causes) will be reported separately.

# 5.4 Primary Outcome Analysis

#### 5.4.1 Primary Analysis of Primary Outcome

The main approach to primary analyses will be an intention-to-treat (ITT), where the ITT population consist of all randomised participants into the trial (regardless of whether they received trial drug). Descriptive statistics of the estimated exacerbations rates in the 48 week treatment period will be presented by treatment arm and overall (Table 5 in Appendix-1). Histogram of the number of exacerbations in the 48 week period by patient will be drawn to check the distribution of the number of exacerbations during treatment (Figure 5). Cumulative number of exacerbations will be plotted by treatment arm (Figure 6).

A generalised linear model (assuming a negative binomial distribution, which accounts for variability among patients in the number of and frequency of exacerbation) will be fitted for the primary outcome of COPD exacerbations during the 48 week treatment period as an outcome with explanatory variables of treatment arm and number of exacerbation in the 12 months prior to the trial (stratification factor), and log-time on study as an offset. The offset (log-time), allows for different lengths of time on treatment for each participant [2]. This assumes that missing data is missing at random (MAR), and will be applied where all of the available observed data are analysed without deletion nor imputation.

The primary outcome data is assumed to follow a negative binomial distribution with the over dispersion estimated to be 1.3. The primary analysis of the primary outcome will give an estimate of the significance of the dispersion parameter. If the dispersion is found to be non-significant (i.e no evidence of over-dispersion) we will consider the simpler Poisson model where the dispersion parameter equals to zero. The ratio of the exacerbation rates (RR) on the anti-ST2 relative to the placebo, associated two-sided 95% confidence interval (CI) and p-value will be reported (Table 5 in Appendix-1). A value of 1.0 would indicate the same rate as placebo; the lower the ratio the greater reduction in exacerbations compared with placebo. A two-sided p-value  $\leq 0.05$  will be considered as a significant difference in the number of COPD exacerbations in 48 weeks between the two treatment arms.

### 5.4.2 Secondary Analyses of Primary Outcome

The secondary analysis of the primary outcome will be carried out on the per-protocol population. In this analysis participants with major protocol deviations (as defined in section 3.1.1) will be excluded from the analysis. All other methods regarding the model construction and presentation will remain the same.

### 5.4.3 Sensitivity Analyses

To examine the sensitivity of the result of the primary analysis to departures from the underlying assumptions (i.e MAR), additional analysis will be performed using the controlled multiple imputation method [3].

# 5.5 Secondary Outcome Analyses

### 5.5.1 Primary Analysis of Secondary Outcomes

All secondary end-points will be analysed using the modified intention-to-treat population, with the exception of adverse events, for which we will analyse the safety population, consisting of all participants who received at least one dose of trial medication.

Descriptive statistics of all the secondary outcomes listed in section 2.2 will be presented by treatment arms and overall by assessment time points (i.e by visit). Numbers (with percentages) for binary and categorical variables and means (and standard deviations), and medians (with lower and upper quartiles) for continuous variables will be presented.

All binary secondary outcomes will be compared between treatment groups using logistic regression. Odd ratio (OR) with two-side 95% CI and P-value will be reported for those outcomes.

All continuous longitudinal outcomes (repeated measurements i.e week 0, 4, 12, 24, 36 and 48) will be compared using mixed effects model with explanatory variables of treatment arm, number of exacerbations in the 12 months prior to the trial (stratification factor), visit number in weeks (categorical) and patient identification as a random effect to account for repeated measures over time. This method will able to handle missing data happening during the follow-up measurements. Adjusted mean differences alongside two sided 95% CI and P-value will be reported for these outcomes. If the distribution of the variable found to be far from normal distribution, a log transformation will be used to modify the non-normality. Adjusted geometric mean difference alongside two sided 95% CI and P-value will be reported.

To compare change from baseline to 48 weeks (pre and post treatment measurements), analysis of covariance (ANCOVA) model with baseline value as a covariate will be used. Adjusted mean differences with 95% confidence interval will be reported if the data are normally distributed. If there is severe departure from normality the first approach will be data transformation with the above technique applied to the transformed data. Adjusted geometric mean difference with 95% CI and P-value will be reported. If the data cannot be transformed to normality then the Mann-Whitney U test will be used and in this case no baseline adjustment will be made.

All safety data will be analysed as described in section 7 of this SAP.

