7.5.1 Method of implementing the randomisation/allocation sequence

Once the participant has given written consent to the trial, a member of the trial team will assess the eligibility of the participant by completing a screening visit. If eligible, randomisation should occur immediately after the participant undergoes their baseline assessment where possible. The unblinded trial personnel (authorised and trained) will complete a randomisation form, enter the eligibility criteria data onto the online system and randomise the participant to a treatment allocation, this will generate a unique participant ID and a blinded randomisation code which relates either to the IMP (anti-ST2 or placebo). The linkage information between the randomisation code list(s) and the allocated treatment will be generated/held by the Sealed Envelope system and by the unblinded trial personnel.

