# **1.3** Visit schedule

#### Table 1: Schedule of Procedures

	L.	Rand	omised	l treatn	nent (vi	sit win	dow +/	- 7 days	5)					Efficacy end point	3 month post- trial follow-up	Withdrawal	Unscheduled visit
Trial assessment	Screen												(visit window +/- 7 days)			(e.g. exacerbation)	
	V0	V1	V2	V3	V4	V5	V6	V7	V8	V9	V10	V11	V12	V13	V14 +/- 14 days		
		Wk 0	Wk 4	Wk 8	Wk 12	Wk 16	Wk 20	Wk 24	Wk 28	Wk 32	Wk 36	Wk 40	Wk 44	Wk 48	Wk 60		
Consent	х																
Review Inclusion & Exclusion	х	х	х	х	х	х	х	х	х	х	х	х	Х	х	х	x♦	x♦
Randomisation		х															
Dosing		х	х	х	х	х	х	х	х	х	х	х	Х				
Demographics (age, gender, BMI, ethnicity, smoking status)	x																
Vital signs (pulse, BP, temp, O 2 sats)	х	x	х	х	х	х	x	х	x	х	x	х	Х	X^	x^	x♦	x♦
Medical history	х																
Concomitant Med	х	х	х	х	х	х	х	х	х	х	х	х	Х	х	х	x♦	x♦
Physical examination	х	х													x^		x♦
Safety AE/SAE		х	х	х	х	х	х	х	х	х	х	х	Х	х	х	x♦	x♦
COPD ** Exacerbation frequency			х	х	х	х	x	х	x	х	х	х	Х	x	x		x♦
SGRQ-c		х	х		х			х			х			x^	x^	x♦	x♦
mMRC	х	х	х		х			х			х			x^	x^	x♦	x♦
CAT		х	х		х			х			х			x^	x^	x♦	x♦
VAS (dyspnoea, cough, sputum)		х	х		х			х			х			x^	x^	x♦	x♦
Sputum Purulence Colour Card	х				х			х			х			x^	x^	X.	x♦

ST-QRD-1 v2

Author: [name] Page 13 of 36

Trial assessment	Screen	Rand	omised	treatm	nent (vi	sit wind	dow +/-	- 7 days	5)					Efficacy end point (visit window +/- 7 days)	3 month post- trial follow-up	Withdrawal	Unscheduled visit (e.g. exacerbation)
	V0	V1	V2	V3	V4	V5	V6	V7	V8	V9	V10	V11	V12	V13	V14 +/- 14 days		
		Wk 0	Wk 4	Wk 8	Wk 12	Wk 16	Wk 20	Wk 24	Wk 28	Wk 32	Wk 36	Wk 40	Wk 44	Wk 48	Wk 60		
VOC (PTRMS & ADVION)	х				х			х			х			×^	×^		x•
Post- BD spirometry	х		х		х			х			х			×^	^x^	X\$	X+
Pre and post BD spirometry		х												x^			
'Body box'	X+													x^			
HbA1C	х		х		х			х			х			x^	×^		x•
FBC	х		х		х			х			х			x^	×^	X♦	x•
U&Es	х		х		х			х			х			x^	×^	X♦	x•
LFTs	х		х		х			х			х			x^	x^	X.	x•
CRP	х		х		х			х			х			x^	×^	X♦	x•
RNA (PAXgene)	х		х		х			х			х			x^	x^	X.	x♦
DNA (PAXgene)	х																
Total IgE & RAST (HDM, pollen, cat, dog)	x																
Serum/plasma inflam biomarkers	х		х		х			х			х			×^	x^	X♦	x♦
Lipid profile	х													×^			
Pharmacokinetics PK \$		х	х					х						x^			x♦
ADA		х	х					х						×^			x•
Pharmacogenetics SNPs	х													×^			
NTproBNP	х		х		х			х			х			×^	×^	X♦	x•
Participant Diary		х	х	х	х	х	х	х	х	х	х	х	Х	x	х	X.	x♦

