# 6.1 Subgroup Analyses

A subgroup analysis of the primary outcome will be carried out based on baseline blood eosinophil, dichotomised by the median value. The primary outcome of COPD exacerbations in 48 weeks will be summarised by low or high eosinophil count and analysed as described in section 5.4.1. An indicator variable to specify the eosinophil group (low or high) will be added to the analysis model. The additional of an interaction term between eosinophil indicator variable and treatment group will assess the difference in treatment efficacy between low and high eosinophil groups. *Post hoc* the clinically important eosinophil cut-off (>300 eosinophils/ $\mu$ L) was included as an additional subgroup analysis.

Additional subgroup analyses of the SGRQ-C and FEV1 will also be carried out based on the baseline blood eosinophil, dichotomised by the median value. The SGRQ-C sore and FEV1 will be summarised by low or high eosinophil count and analysed as described in section 5.4.1. An indicator variable to specify the eosinophil group (low or high) will be added to the analysis model. The addition of an interaction term between eosinophil indicator variable and treatment group will assess the difference in SGRQ-C score and FEV1 between the low and high eosinophil groups.

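### As worded, the SAP 5.5.1 mixed model counts baseline week 0 as a response, so with complete data its single treatment estimate is expected to be 5/6 of the average effect over weeks 4 to 48

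*SAP*

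**What the plan says.** SAP 5.5.1 gives the rule for repeated measures: "All continuous longitudinal outcomes (repeated measurements i.e week 0, 4, 12, 24, 36 and 48) will be compared using mixed effects model". Besides treatment arm, the explanatory terms are "number of exacerbations in the 12 months prior to the trial (stratification factor), visit number in weeks (categorical) and patient identification as a random effect". One adjusted mean difference per outcome is reported, with a confidence interval and p-value; skewed outcomes are log-transformed.

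The same section adds a second method: "To compare change from baseline to 48 weeks (pre and post treatment measurements), analysis of covariance (ANCOVA) model with baseline value as a covariate". It does not say which outcomes this covers.

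Protocol 7.5.1 says that "randomisation should occur immediately after the participant undergoes their baseline assessment where possible", and the first dose is also at week 0. SAP Table 1 schedules SGRQ-C, CAT, VAS, mMRC and sputum differentials at week 0 and at weeks 4, 12, 24, 36 and 48. The full blood count has a screening value but none at week 0. The row "Sputum Purulence Colour Card" has a screening value but none at week 0 or week 4.

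For the eosinophil subgroups, SAP 6.1 says: "The SGRQ-C sore and FEV 1 will be summarised by low or high eosinophil count and analysed as described in section 5.4.1". Section 5.4.1 is the negative binomial model for exacerbation counts.

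**The concern.** A single arm coefficient in a model with no arm-by-visit term is an average of the arm differences over every visit entered as a response. If week 0 is one of those visits, a difference with expectation zero is averaged in and the estimate shrinks toward no effect.

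The size of the estimate is the main product here. Protocol 10.6 plans estimates with confidence intervals for secondary outcomes, without hypothesis tests unless the SAP says otherwise. SGRQ-C and CAT are named as key secondary outcomes in SAP 5.5.2. The per-protocol analysis there keeps the same model, and 5.5.3 plans no sensitivity analysis for secondary outcomes, so neither would expose the shrinkage.

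The pointer in 6.1 is a separate fault. SGRQ-C and FEV1 are continuous measurements, and a count model with log time as offset does not fit them.

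**Working it through.** The documents give no figure for this model, so there is none to reproduce.

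**Inputs.** Six response visits (SAP 5.5.1: weeks 0, 4, 12, 24, 36, 48); terms as listed in 5.5.1; 1:1 allocation (Protocol 7.5); expected arm difference of zero at week 0 (Protocol 7.5.1).

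**Expectation, complete data.** With a random intercept and categorical visit, the generalised least squares arm coefficient is the plain mean of the six visit-specific arm differences. Write d4, d12, d24, d36 and d48 for the post-dose effects:

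- E(coefficient) = (0 + d4 + d12 + d24 + d36 + d48)/6 = 5/6 × the weeks 4–48 average = 0.833 of it.

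An exact calculation gave 0.8333 at within-patient correlations of 0.4, 0.6 and 0.8, for both a constant and a growing effect. This is an expectation: in one trial, one sixth of any chance week-0 imbalance also enters the estimate.

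**Log scale.** The factor applies to the log ratio. A true geometric mean ratio of 0.70 becomes 0.70^(5/6) = 0.743; 0.50 becomes 0.50^(5/6) = 0.561.

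**Week 48 lost for everyone, weeks 0–36 kept.** E = (0 + d4 + d12 + d24 + d36)/5 = 4/5 of the weeks 4–36 average. The same figure applies to sputum counts if they follow Protocol 3.5.2, which lists inflammation only to week 36.

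**Null case.** If every effect is zero, the expectation is zero. Simulated rejection under the null was 4.5% to 5.1% (10,000 runs per correlation).

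**Power, illustration only.** Assumptions not in the documents: effect 0.5 SD, compound symmetry, complete data, correlation ρ from 0.3 to 0.8. n = 36 per arm (80 less 10% drop-out is 72, halved). Variances in SD units:

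- as worded: 2[ρ + (1−ρ)/6]/n, expected estimate 0.5 × 5/6 = 0.417
- week 0 removed from the responses: 2[ρ + (1−ρ)/5]/n, expected estimate 0.5
- baseline covariate also added: 2[ρ + (1−ρ)/5 − ρ²]/n, expected estimate 0.5

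Example at ρ = 0.5, as worded: SE = √(2 × 0.5833/36) = 0.180; power = Φ(0.417/0.180 − 1.96) = 0.64.

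| ρ | as worded | week 0 removed | baseline also added |
|---|---|---|---|
| 0.3 | 78% | 89% | 95% |
| 0.5 | 64% | 78% | 95% |
| 0.7 | 53% | 68% | 98% |
| 0.8 | 49% | 64% | over 99% |

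The first step, 11 to 15 points, is the dilution. The second is precision gained from the covariate and is a separate matter. Simulated mean estimates as worded were 0.414 to 0.418, against the expected 0.417.

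**The case against.** **The wording may be loose.** The list of weeks repeats the measurement schedule in SAP 2.2.1, and 5.5.1 speaks of missing data during follow-up, so the author may have meant week 0 as baseline only. That is possible. But the SAP writes a baseline covariate where it wants one, in the ANCOVA, and an interaction where it wants one (6.1: "The addition of an interaction term between eosinophil indicator variable and treatment group"). Nothing in it gives week 0 another role in the mixed model. The point stands for the model as worded.

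**The ANCOVA already gives an undiluted estimate.** It does, if it is run for SGRQ-C, CAT and the rest. SAP 1.1.4 words the SGRQ-C subgroup objective as a change, which would suit it. But its outcomes are not named, and Table 1 suspends these week-48 assessments during COVID-19 restrictions. How much week-48 questionnaire or sputum data was lost is not stated.

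**Stronger readings that the documents do not support.**

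- A reader might infer that losing week 48 brings the estimate to 4/5 of the weeks 4–48 average. That needs a constant effect. With effects rising evenly from 0.2 to 1.8 (weeks 4–48 average 1.0), the weeks 4–36 average is 0.8 and the ratio is 0.8 × 0.8 = 0.64. With the mirror-image fading effect it is 0.8 × 1.2 = 0.96.
- A reader might interpolate for partial loss of week 48. SAP 3.3 defines the modified intention-to-treat set as complete case, while 5.5.1 says the mixed model copes with missing follow-up. If patients without week 48 are excluded, the remainder have complete data and the factor stays at 5/6. No partial-loss figure applies until the two are reconciled.
- A reader might infer that the eosinophil-by-treatment interaction is diluted too. Section 6.1 does not point to the mixed model, so this does not follow.
- A reader might see the schedule row "Post- BD spirometry" at weeks 4 to 48 and call the lung-function list in SAP 2.2.1 (weeks 0 and 48) an error. It is not: that list is for pre- and post-bronchodilator spirometry together, and the schedule row for that pair is marked at exactly weeks 0 and 48.

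**Conclusion.** The concern holds for the model as worded. For SGRQ-C, CAT, VAS, sputum counts, and mMRC if treated as continuous, the mixed-model estimate is expected to be 5/6 of the weeks 4–48 average effect, on the log scale where outcomes are logged. This rests on week 0 entering as a response, no arm effect at week 0, and complete data. It does not depend on the SD, the correlation or the shape of the effect over time. The 4/5 figure is relative to the weeks 4–36 average and needs week 48 lost for everyone with earlier visits kept.

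Blood counts and the colour card fall outside the claim unless a screening value is entered as week 0. The primary outcome and type I error are untouched, and the error is toward no effect. The power figures depend on the assumed effect and correlations and show only the order of magnitude. The wrong pointer in 6.1 is certain on its face. Both should be corrected; neither threatens the trial's main conclusion.

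**What to change.** 1. In SAP 5.5.1, take weeks 4–48 as the responses, with arm, visit, arm-by-visit, the baseline value and the stratification factor as fixed effects, keeping the random patient effect. The alternative is to keep week 0 as a response with arm means constrained equal there, plus arm-by-visit. Commit to one in writing.
2. Report the average over weeks 4–48, with week 48 alongside.
3. State which outcomes the week-48 ANCOVA covers.
4. Reconcile the complete-case definition in 3.3 with the statement in 5.5.1 on missing follow-up.
5. In 6.1, replace the pointer to 5.4.1 with the corrected mixed model for SGRQ-C and with whichever 5.5.1 model applies to FEV1, keeping the eosinophil-by-treatment interaction.
6. Reconcile the adjustment with Protocol 10.9, which says that outcomes other than the primary are unadjusted in the main analyses.

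The cost is SAP wording and re-run code, with no new data. The revision history shows that the current SAP version follows database lock and review of the draft report. The change must therefore be labelled post-lock, justified under SAP 6.2, and reported beside the results of the model as signed off.

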7.5 The randomisation scheme

The LCTU will supply a web based randomisation system from a third party (Sealed Envelope Ltd.). Participants will be randomised in a 1:1 ratio to anti-ST2 or placebo, this will be set up as a blinded randomisation process. Each participant will be given a unique screening number on consent, and a unique participant ID when they are randomised. This combination of unique screening number and participant ID will be linked on the enrolment log with the unique participant ID number being used to identify the individual participant throughout the trial following randomisation. Neither of these numbers will be re-assigned to any other subject. Participants will be assigned to trial treatment in accordance with the randomisation schedule.

Randomisation will be stratified by frequency of exacerbation in the previous 12 months (Low [2 or 3] or High [4 or more]). Randomisation results will be printed out and signed as confirmation by the unblinded trial personnel performing the randomisation and a copy will be stored securely with the unblinded documentation and presented to pharmacy alongside the prescription.

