10.9 Adjusted analysis

The analysis of the primary outcome measure (frequency of exacerbations) will take account of the frequency of exacerbation in the previous 12 months, which is used as a stratification factor at randomisation. Analyses for other outcomes will be unadjusted in the main analyses and will only be adjusted in sensitivity analyses if specified by the statistical analysis plan.

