# 5.5.3 Sensitivity Analyses

There will be no sensitivity analyses carried out for any secondary outcome measures.

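### The week-48 ANCOVA omits the stratification factor that the mixed model includes, and neither model matches protocol 10.9, so reported intervals may be slightly too wide

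*SAP*

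**What the plan says.** Protocol 7.5 sets the design: "Participants will be randomised in a 1:1 ratio to anti-ST2 or placebo", and "Randomisation will be stratified by frequency of exacerbation in the previous 12 months (Low [2 or 3] or High [4 or more" are the two levels. SAP 5.4.1 carries this factor into the primary negative binomial model.

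For secondary outcomes, SAP 5.5.1 treats the factor differently by model:

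- The mixed model for repeated continuous outcomes has treatment arm, "number of exacerbations in the 12 months prior to the trial (stratification factor), visit number in weeks (categorical") and a random patient effect.
- For change to week 48, "analysis of covariance (ANCOVA) model with baseline value as a covariate will be used". The stratification factor is not named.

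Protocol 10.9 adjusts the primary outcome for prior exacerbation frequency and then says: "Analyses for other outcomes will be unadjusted in the main analyses and will only be adjusted in sensitivity analyses", and even those only if the SAP specifies them. SAP 5.5.3 specifies none: "There will be no sensitivity analyses carried out for any secondary outcome measures".

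The outcomes that fall most naturally to the ANCOVA are those SAP 2.2.1 lists at weeks 0 and 48 only: spirometry and body plethysmography.

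**The concern.** When randomisation is stratified, the design removes between-stratum variation from the treatment comparison. A linear model without the stratum leaves that variation in its residual, so it reports a larger standard error than the estimate really has. The mixed model avoids this and the ANCOVA in the same section does not, with no reason given.

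Protocol 10.6 makes estimates with confidence intervals the default secondary result, so interval width is what readers will use. Week-48 lung function is also already thinned, because the schedule footnotes cancel visit-13 spirometry and plethysmography during COVID-19 restrictions.

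In addition, the protocol and the SAP do not give the same adjustment rule for secondary outcomes.

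**Working it through.** **Adjustment rules side by side**

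| Source | Baseline covariate | Stratification factor |
|---|---|---|
| SAP 5.5.1 mixed model | no separate covariate; week 0 is among the repeated measurements | yes |
| SAP 5.5.1 week-48 ANCOVA | yes | no |
| Protocol 10.9, main secondary analyses | no | no |

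Taken at its word, protocol 10.9 is departed from by both SAP models: the mixed model through the stratum, the ANCOVA through baseline.

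**Size of the effect on the ANCOVA**

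The plan has no figure to reproduce here. It states no standard deviation, standard error or power for any secondary outcome.

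Inputs: 1:1 allocation and a two-level stratum (Protocol 7.5); N = 80 × (1 − 0.10) = 72 (Protocol 10.1). *Assumption:* the stratum explains a share R² of the residual variance after baseline. The documents give no value, so a range from 0 to 10% is shown.

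- Ratio of reported SE, without to with the stratum = 1/√(1 − R²)
- Actual level of a nominal 5% two-sided test = 2 × [1 − Φ(1.96/√(1 − R²))]

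| R² | SE ratio | Reported SE too large by | Actual level |
|---|---|---|---|
| 0 | 1 | 0% | 5.0% |
| 0.02 | 1/√0.98 = 1.010 | 1.0% | 4.8% |
| 0.05 | 1/√0.95 = 1.026 | 2.6% | 4.4% |
| 0.10 | 1/√0.90 = 1.054 | 5.4% | 3.9% |

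**Check by simulation**

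Stratified permuted-block trials were simulated with N = 72. Further assumptions: block size 4, baseline–outcome correlation 0.7, half the participants in the High stratum.

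| R² | Reported SE, without / with stratum | Ratio | True SD of estimate, without / with | Type I error, without / with |
|---|---|---|---|---|
| 0 | 0.1690 / 0.1689 | 1.000 | 0.1704 / 0.1704 | 0.050 / 0.051 |
| 0.05 | 0.1691 / 0.1646 | 1.027 | 0.1637 / 0.1635 | 0.043 / 0.048 |
| 0.10 | 0.1688 / 0.1603 | 1.053 | 0.1616 / 0.1613 | 0.040 / 0.051 |

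The ratios agree with the formula. They are almost the same at N = 40 (1.027 and 1.054 at R² = 0.05 and 0.10), so loss of week-48 data does not alter the proportion. The true SD column barely moves: the estimate is as precise either way, and only the reported SE differs.

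**The case against.** **Protocol 10.9 may be narrower than it looks.** In context it concerns prior exacerbation frequency. Read that way, the ANCOVA complies and only the mixed model departs. This reading is fair, but 10.9 and SAP 5.5.1 still disagree and the two continuous models still differ from each other.

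**The effect is small and rests on an assumption.** If the stratum tells us nothing beyond baseline, nothing changes. This stands. Type I error also matters little, since protocol 10.6 defaults to intervals without tests and SAP 5.5.1 mentions no p-value for the ANCOVA on normally distributed data.

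**The reach is limited.** SGRQ-c and CAT are repeated measures and fit the mixed model. Post-bronchodilator spirometry is also scheduled at weeks 4, 12, 24 and 36, so post-bronchodilator FEV1 is not clearly an ANCOVA outcome. This stands too.

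A reader might also infer four stronger points that the documents do not support:

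- *The logistic models have inflated standard errors too.* SAP 5.5.1 says "All binary secondary outcomes will be compared between treatment groups using logistic regression", with no covariates named, but SAP 2.2.1 defines no outcome as binary. The direction is also opposite. In simulation at N = 80, adding the stratum raised the SE of the log odds ratio from 0.471 to 0.487 (stratum odds ratio 2) and from 0.468 to 0.512 (stratum odds ratio 4), with similar rejection rates (0.677 and 0.678; 0.617 and 0.636). Omission gives a marginal rather than a conditional odds ratio.
- *Precision is lost, as if participants were discarded.* The true SD is 0.1637 without the stratum and 0.1635 with it at R² = 0.05.
- *SAP 5.5.3 contradicts protocol 10.9.* It does not: 10.9 allows adjusted sensitivity analyses only where the SAP specifies them, and the SAP specifies none.
- *Every secondary model needs baseline and stratum added.* The mixed model already has week 0 among its outcomes, and a Mann-Whitney test takes no covariates.

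**Conclusion.** The point holds in a limited form. SAP 5.5.1 is inconsistent about the stratification factor, and its two continuous models do not match protocol 10.9 as written. For the week-48 ANCOVA, the reported standard error and interval width are about 1.0%, 2.6% or 5.4% too large under assumed partial R² of 2%, 5% or 10%, and correct if the stratum has no association with the outcome after baseline. The error is conservative and unbiased, touches secondary outcomes only, and leaves the estimate's true precision essentially unchanged. Including the factor is a free improvement; its omission does not invalidate the analysis.

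**What to change.** 1. In SAP 5.5.1, add the Low/High stratification factor to the week-48 ANCOVA alongside the baseline value.
2. Amend protocol 10.9 so that it agrees with the SAP's adjusted continuous models.
3. Record the change, its reason and its timing, as protocol 10.13 and SAP 6.2 require. The SAP revision history shows that version 2.1 followed database lock and review of a draft analysis report, so a change made now must be identified as made after lock.

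Leave the covariates of the mixed model and the Mann-Whitney fallback as they are.

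Cost: short wording changes in two documents with the usual version control, a note in the statistical report, and one degree of freedom. No new data are needed.
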